- a) **RECRUITMENT AND SCREENING:** We will enroll 32 dementia at-risk seniors over 2 years. **Our sample size is not based on demonstrating clinical efficacy but to obtain preliminary data and feasibility to plan our R01.** We will contact a random sample of individuals age 65 and over identified from local population lists as well as from the large clinical population in our health system. Both sources were used to recruit ~3000 participants for our aging studies.³⁵⁻³⁷ A letter explaining our study is followed by a telephone call. Those expressing interest on the telephone are screened with Memory Impairment screen (**MIS**)³⁸ and **AD-8**³⁹ to establish dementia-risk status. Potential recruits will be invited for an in-person visit where final eligibility is determined. Written consent and screening is at our research center. **An independent DSMB will be constituted prior to the start of the study.**
- b) **ELIGIBILITY CRITERIA.** Our target population is dementia at-risk seniors. Patients will be evaluated by research assistants followed by the study clinician to assess eligibility for the trial.

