 - i) Inclusion criteria: **1)** Age 65 and older. **2)** 'At-risk for dementia' status defined as meeting cutscores on either MIS (≤ 6) or AD-8 (≥ 1) tests. The MIS is a 4-item dementia screener developed in our Bronx population.^{38, 40} MIS accounts for various educational levels.⁴¹⁻⁴⁴ The AD-8 is a 2-minute screener with high validity for detecting dementia.^{39, 45} AD-8 is less educationally biased as it does not test patients on acquired learning. AD-8 is culturally neutral as it focuses on changes in basic activities in which everyone engages. Both tests correlate highly with dementia pathology.^{46, 47} We used these 2 screeners to enroll 3000 participants in 3 NIH funded studies.^{38, 48, 49} We decided against MCI as a criterion, as its prevalence is low (<12% in our community-based cohort⁵⁰); limiting generalizability. We examined validity of our '**dementia at-risk**' definition in 543 older adults in the Einstein Aging study;⁴⁸ 176 met dementia at-risk criteria (prevalence 32%). Over a mean follow-up of 1.5 years, 'dementia at-risk' status predicted incident cognitive impairment (any of MCI, Motoric cognitive risk syndrome (MCR)^{51, 52} or dementia) (HR adjusted for age, sex, education and illnesses 2.0, 95%CI 1.1-3.8). Hence, our definition captures a high-risk yet highly prevalent group. **3)** Sedentary: exercises less than the CDC recommended level of 150 min moderate intensity activity/week.⁵³ **4)** Agree to neuroimaging: more efficient to enroll those who also meet imaging criteria for this pilot. We recruited >100 participants in the last 2 years for various imaging studies.
 - ii) Exclusion criteria: **1)** Active medical or major psychiatric illnesses. **2)** Musculoskeletal/cardiovascular mobility limitations. **3)** Competitive dance or regular social dance (>1/month). As seniors may occasionally dance at social events (but not at dose for cognitive benefits), excluding all seniors who ever danced is not practical. **4)** Presence of dementia¹⁰⁶ (telephone or in-house evaluation). **5)** Standard imaging exclusions. It will not be feasible to obtain MRI or other biomarkers to screen and enroll participants. However, the pre-intervention MRI for Aim 2 will allow us to stratify the at-risk group into those with or without brain pathology (e.g. hippocampal atrophy⁵⁴) for exploratory analyses.

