- c) **RANDOMIZATION.** Eligible participants are randomized for interventions at initial visit, stratified by gender and age (< or >80 years). Equal number of men and women will be enrolled. Group assignment is generated by [name], who is not involved in subject testing or interventions. She will generate an encrypted file with the randomization order to assign participants to the study arms. She will be the only one with access to the list. To avoid attrition following enrollment, we will not wait to recruit all participants to start the interventions but will have rolling admission into the dance and walking classes.

- i) **Social Dance (intervention arm):** 90-min dance sessions twice weekly for 6-months. The session includes warm-up, dance and cool down. The program includes Foxtrot, Waltz, and Latin dances. The choice of multiple dances is pragmatic since it mirrors the choice offered in senior centers and avoids tedium of only doing one dance form. Intensity will not be manipulated to mimic exercise training as in aerobic dance classes. Dance instructors are experienced in teaching seniors (see LOS from USA Dance). Progression to new dances will be gradual and take into account balance, cardiac and cognitive demands. Methodological structure is the same for all sessions. The instructor will demonstrate the dance sequence. Participants warm up with gentle stretches. The instructor will repeat dance sequence several times and the participants will try to reproduce it along with the instructor, until sequence is learned. When participants execute the dance sequence satisfactorily, they will reproduce it along with the music.
- Duration (6 months), frequency (2/wk) and intensity** based on earlier dance studies and pragmatic considerations. A review of dance interventions for various health outcomes (including cognition) concluded that dance programs should provide a minimum of one 45-minute session per week for 6 weeks (lower than our study).⁵⁵ The dose of exercise in both dancing and walking arms is higher than the CDC recommended exercise dose.⁵³
 - Pairing** at dances is at random and the instructor will ensure participants rotate partners.
 - Performance monitoring:** Intensity measurement via **accelerometers** and cardiac monitoring during dance lessons.

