- d) **OUTCOMES Aim 1 (Cognition):** As EF includes multiple cognitive processes; a single test is not sufficient. We will examine a **composite EF score** by summing standardized scores on the 3 tests. Composite cognitive scores were used in many RCTs.²¹⁻²³ We will also compare trajectories in individual tests to gain insights into study design of our full-scale RO1. Study outcomes will be assessed at baseline, month 2, month 4, post-intervention (end of month 6), and 3 months post-intervention (month 9).

- i) **Digit Symbol Substitution test (DSST)** is a timed test that assesses speed of processing, visuo-spatial attention and EF. DSST predicts cognitive (dementia) and non-cognitive outcomes (falls). DSST is amenable to exercise.⁶⁹
- ii) **Flanker Test** is in the NIH toolbox.^{19, 20} It measures attention and inhibitory control. The Flanker test was used to demonstrate exercise effects on EF.^{8, 70}
- iii) **Walking While Talking test (WWT)** is an EF-dependent everyday behavior measure developed by our group.^{29, 30} Dual-tasking assessed by WWT is a defined facet of EF,^{36, 71} and associated with increased prefrontal activation.⁷² Participants walk on an instrumented walkway for 2 trials reciting alternate letters of the alphabet.⁷³ See our published papers for WWT procedures.^{28-30, 72-74} WWT has excellent test-retest and inter-rater reliability.²⁸⁻³⁰

Blinding: While double-blinding both subjects and testers is not feasible, the following steps (besides randomization) are included: A. Selection bias reduced by concealing treatment allocation until subject enrolled.⁷⁵ B. Outcome is an objective endpoint and not subjective reports.⁷⁵ C. Dance and walking groups meet non-overlapping times. D. Each aspect of the RCT is supervised independently: interventions ([name]), assessments ([name]) and imaging ([name]). E. Participants/staff instructed not to disclose group assignment or interventions.

Learning effects: We will utilize 4 complementary approaches to attenuate practice effects⁷⁶: (1) Practice pre-baseline to reduce task familiarity effects; (2) Item-specific driven improvements minimized by using tasks with multiple similar items and standardized encoding; (3) We developed alternate forms for the WWT task,⁷⁴ and alternate forms of the DSST are available; and (4) use of control group.

- e) **OUTCOME Aim 1 (Feasibility):** Metrics below will identify barriers and refine design of our full scale RCT.⁷⁷

Metric	Measurement	Comments

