 - viii) **Active psychoses or psychiatric symptoms** (such as agitation) noted during the clinic visit that will prevent completion of study protocols. Past history of these symptoms or presence of psychiatric illness not used as exclusion criteria.
 - ix) **Either participation in competitive dancing or recreational dancing at a frequency >1/month in the past six months.** As seniors may dance at social events (but not at doses or frequency to have cognitive benefits), excluding all seniors who ever danced is not practical. We will examine all reports of participation in cognitive enhancement programs (as this covers a wide range of activities) to judge inclusion.
 - x) **Participation in other interventional study that overlaps with intervention period of this study.**
- d) Specific Neuroimaging considerations: Additional exclusions relevant to neuroimaging include the presence of any surgically implanted metallic devices, such as aneurysm clips or pacemakers that would be a safety contraindication for MRI. Subjects with large amounts of dental or surgical hardware in the head and neck will be excluded because magnetic susceptibility effects will lead to severe image artifacts in these subjects' images. Due to the confined space of the MRI magnet, subjects with a known history of claustrophobia will also be excluded as will subjects with weight >350lbs or waist circumference >55 inches. Conditions that may confound the association between neuroimaging

cognition and mobility (normal pressure hydrocephalus or severe head trauma) will be excluded from analyses. We estimate that the prevalence of these conditions is very low based on other aging studies. Additional incidental findings that may be seen with a low prevalence in the elderly may include vascular anomalies or tumors. All scans will be reviewed by board-certified neuroradiologists. Abnormal results will be communicated to [name] who will initiate follow-up with subjects and their physicians as has been our established procedure in other studies based in our center.

- e) Recruitment, enrollment, and participation of participants in this project are not limited by gender, skin color, racial/ethnic group, or economic status. We will monitor recruitment and retention patterns to ensure adequate representation of women and minorities.

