- f) **Research material** obtained from human subjects will be the results of clinical and neuropsychological testing obtained from study assessments and telephone interviews. The subject and their primary care physician will be informed of all clinical results that are relevant to patient care. Phenotypic data will also include results of MRIs, questionnaires, and body composition tests.

5) Participant Recruitment

- a) To achieve our study aims 32 participants will be recruited at random from commercially available lists of Bronx and Westchester County residents over the two-year funding period. We will also recruit participants from the Montefiore Medical Center Geriatrics and primary care clinics that have over 20,000 visits by patients, age 65 and older. We have had experience using both the community and clinic sources to recruit over participants for various aging studies in the past 10 years. Once telephone contact is achieved and the interview is complete, we assume that there will be a 20% loss due to lack of interest in the study and failure to meet general eligibility requirements and an additional 10% failure on the cognitive instruments (MIS or AD-8). There is an additional 10% loss in the remaining sample due to failure to meet eligibility requirements. Using telephone based recruitment instruments enables us to minimize loss due to not meeting criteria on in-person assessments.

A concern is that there might be attrition between the enrollment and start of the intervention in this high-risk group. To minimize this possibility, we will institute a rolling admission policy that we have successfully used in our ongoing cognitive remediation study.¹¹⁴ A different dance is taught in each session. As soon as we have enrolled a pair into the dance group, they will start the dance program in the next available day. This modified rolling admission policy will help reduce delays between enrollment and the start of the dance intervention. In the walking group, the intervention is individualized though participants exercise in groups on the treadmill to simulate the social nature of dancing. Hence, participants randomized to the walking arm can join the walking program at any point during the 2-year study period. Participants randomized to the walking group will also start the program at the next available day.

6) Informed Consent

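### Randomizing at the initial visit lets the baseline MRI for Aim 2 fall after participants know their arm; assignment should follow the baseline assessments

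*Combined protocol and SAP*

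**What the plan says.** Section 2) c) Randomization: "Eligible participants are randomized for interventions at initial visit, stratified by gender and age". Section 2) a) Recruitment and Screening: "Potential recruits will be invited for an in-person visit where final eligibility is determined". Assignment is thus tied to the visit that settles eligibility.

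Section 2) b) ii) Exclusion criteria: "It will not be feasible to obtain MRI or other biomarkers to screen and enroll participants". It goes on to say that "the pre-intervention MRI for Aim 2 will allow us to stratify the at-risk group" by brain pathology. The scan is dated relative to the intervention, not to assignment.

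Section 2) d), under Blinding: "While double-blinding both subjects and testers is not feasible", and "Selection bias reduced by concealing treatment allocation until subject enrolled". Concealment is promised up to enrolment and no further.

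Section 5) a) says that once a pair has been enrolled in the dance arm "they will start the dance program in the next available day". Walkers may join at any time and also start on the next available day.

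Section 8) b) makes the month 0 versus month 6 imaging comparison the Aim 2 analysis, and section 2) f) names task-based fMRI as the primary imaging measure. Section 4) d) lists imaging contraindications, known claustrophobia and body-size limits as exclusions. Separately, it says that people with certain confounding conditions ("normal pressure hydrocephalus or severe head trauma) will be excluded from analyses") are removed at analysis. Section 8) c) on missing data mentions contact persons and flexible make-up sessions. It has no rule for a failed or refused baseline scan.

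**The concern.** A baseline measured after assignment is protected only if participants do not know their arm or cannot influence the measurement. Neither holds here. People will know whether they are to dance or walk, and the task fMRI baseline depends on engagement. Section 2) f) gives 12 minutes for the imagined walking-while-talking task, about 10 for the DSST and 4 + 3 × 4 = 16 for the Flanker task. That is about 12 + 10 + 16 = 38 minutes if practice is run in the scanner, before any diffusion imaging. Effort, tolerance and willingness to attend could differ with how pleased someone is with the assignment.

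Two things are at stake, mainly in Aim 2. An arm-related difference in the baseline scan would enter the estimated change. And a person who declines the scan after assignment is a post-randomization loss, when the same refusal before assignment would simply mean that the person is not randomized.

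**Working it through.** **1. Order of events.**

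| Step | Section | What is fixed |
|---|---|---|
| Final eligibility | 2) a) | At the in-person visit |
| Randomization | 2) c) | At the initial visit, once eligible |
| End of concealment | 2) d) | At enrolment |
| Baseline MRI | 2) b) ii) | Not used to screen and enrol; before the intervention |
| First session | 5) a) | Next available day; dance waits for a pair |
| Baseline DSST, Flanker, WWT | 2) d), 8) | At baseline; order relative to assignment not given |

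If eligibility and assignment share a visit and the scan is not part of enrolment, the scan falls between assignment and the first session. This is an inference from several sections; no schedule states it.

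**2. How a baseline shift would act.** The unadjusted Aim 2 contrast is (post − pre in dance) − (post − pre in walking). A shift δ in the dance arm's baseline mean changes it by −δ, in full. The sign is unknown: extra effort at baseline in the preferred arm would understate that arm's gain. The month 6 group difference, which section 8) b) also reports, does not contain the baseline scan. The documents give no basis for a value of δ, so none is offered.

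**3. Loss of paired scans.** Aim 2 has no stated effect size or detectable difference to reproduce. Section 8) b) gives only 16 per group, with no allowance for scan failure. The Aim 1 slope figure is not an input here.

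Inputs: 16 per arm; 20% dropout (section 8) a), Power); 20–25% attrition (section 2) e), feasibility table). The share f with no baseline scan, whether failed or refused, is **assumed** at 5% to 20%.

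- Paired scans per arm: n = 16 × (1 − dropout) × (1 − f)
- Detectable difference in SDs of change (80% power, two-sided 0.05, normal approximation): 2.80 × √(2/n)
- Chance of at least one missing baseline scan among 32: 1 − (1 − f)^32

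| f (assumed) | Expected missing of 32 | Chance of ≥1 | n per arm, 20% dropout | Detectable | n per arm, 25% dropout | Detectable |
|---|---|---|---|---|---|---|
| 0 | 0 | 0 | 12.8 | 1.11 | 12.0 | 1.14 |
| 5% | 1.6 | 81% | 12.2 | 1.14 | 11.4 | 1.17 |
| 10% | 3.2 | 97% | 11.5 | 1.17 | 10.8 | 1.21 |
| 20% | 6.4 | >99% | 10.2 | 1.24 | 9.6 | 1.28 |

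The precision cost is modest: the detectable difference grows by 1/√(1 − f), about 3% at f = 5% and 12% at f = 20%. But some missing baseline scans are likely at any of these rates, so a rule is needed. Imbalance could matter more than the total: 3 losses are 3/32 = 9% of the sample, but 3/16 = 19% of an arm if all fall in one.

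The table covers all causes. Moving assignment later avoids only the part due to refusal or withdrawal between assignment and scan. Technical failures would still occur, but before anyone knew their arm.

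**The case against.** **The order is inferred.** The sentence on MRI feasibility can be read as declining MRI as an eligibility biomarker, not as dating the scan, and the documents do not say when participants learn their arm. This stands as a limit on certainty. But nothing places the scan before assignment, so a site following the text may randomize first.

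**The entry criteria already remove much of the loss.** Agreement to MRI is required, and contraindications and known claustrophobia are excluded. This also stands. What remains is in-scanner failure, later refusal and unusable data, and technical failure is unlikely to depend on arm.

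**A reader might infer that the Aim 1 EF baseline is compromised too.** The documents do not support that. Section 6) a) has cases diagnosed and excluded after clinical and neuropsychological testing, so some cognitive testing precedes assignment. Whether that includes the DSST, Flanker and WWT is unstated. Aim 1 EF needs no scan, and Aim 1 also covers feasibility and differences at each time point, so not every estimate is a change from baseline.

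**A reader might also infer that the section 4) d) exclusion biases the comparison.** The named conditions pre-exist assignment, their prevalence is described as very low, and the text sits under a neuroimaging heading. The fault is only that its scope is not stated.

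**Requiring a usable, read scan before assignment would create the MRI gate that section 2) b) ii) calls infeasible.** At the assumed failure rates it would take about 32/(1 − f) = 34 to 40 people scanned to randomize 32. This stands, and the fix avoids it.

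**Conclusion.** The point holds for Aim 2. As written, the plan allows the month 0 fMRI and diffusion values to be collected, or declined, after unblinded assignment. Any arm-related shift would pass in full into the unadjusted difference in change, with unknown sign and size. At assumed failure or refusal rates of 5% to 20%, 1.6 to 6.4 of the 32 randomized would lack a baseline scan, and the detectable difference in change at 20% dropout would rise from 1.11 to between 1.14 and 1.24 SD. Only part of that loss is avoidable by reordering.

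It would go too far to say that the randomized comparison is broken. The scan still precedes the intervention, entry criteria limit refusals, and this is a pilot meant to estimate effects for a larger trial. For Aim 1 the finding is an unstated order, not a demonstrated bias. The conclusion rests on reading the eligibility, MRI, randomization and blinding text together. A schedule showing the scan before assignment would remove it.

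**What to change.** Reword section 2) c) along these lines: *eligible participants are randomized after the baseline DSST, Flanker and WWT and after the baseline MRI session has been attempted; sessions start on the next available day.* The scan need not be usable, need not have been read and does not act as an eligibility screen. Someone who attempts it without success is still randomized. Someone who no longer agrees to MRI before assignment no longer meets that entry criterion and counts as a pre-randomization loss.

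Also state that:

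- all randomized participants stay in the Aim 1 EF analysis;
- the section 4) d) removal for confounding conditions applies to imaging analyses only;
- missing or unusable baseline scans are reported by arm, with reasons.

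The cost is protocol wording and scheduling. The MRI must precede the intervention in any case, so reordering adds little or no time before the first session, and rolling admission continues as in section 5) a). No extra scans are needed by design, though anyone scanned and then lost before assignment would have to be replaced. The downside is that assignment comes some days after consent, and drop-outs in that gap count as pre-randomization losses. They should be reported, since recruitment and retention are feasibility outcomes.

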1.0 Participants Safety

1.1 Potential Risks and Benefits for Participants

Potential Risks: We do not expect any serious adverse events during these non-invasive tests and training programs of attention and executive function. Answering health questionnaires and mental state examinations involve minimal psychological, social, or other risks.

Dance classes will be taught by certified dance instructors (with experience teaching seniors) at varying levels of complexity and the progression during the intervention period will be gradual. Progression to new dances will take into account the balance challenge, cardiovascular demand, degree of flexibility, coordination and cognitive demand. The instructor will ensure that the programs will not be manipulated to mimic exercise training as in aerobic dance classes.

The treadmill training walking intervention protocol will be based on recommendations of the American College of Sports Medicine (ACSM)¹⁰⁶ and American Heart Association (AHA) for older adults. A gradual approach will be applied to increase exercise intensity in participants with a low baseline level of physical activity and who

may be unfamiliar with treadmill walking. Pulse and blood pressure will be assessed before and after each session to assure that the values are not deviated by 10 or more from the values of initial assessment for pulse and systolic blood pressure. During exercise, participants are monitored with the subjective Borg scale⁶⁸ every 5 minutes and heart rate is tracked by a physical therapist. Participants are encouraged to increase the training velocity if the subjective rating of exercise intensity is low (fairly light, Borg score <12). The treadmill speed will be reduced or exercise aborted if there are any untoward symptoms such as cardiovascular symptoms or excessive fatigue. Heart rate will be measured during the break between training periods and the second period will only be initiated after the value is below the 70% of estimated maximum heart rate.¹⁰⁶ Similar procedures will also be followed in the dance intervention group.

Potential Benefits: Our previous experience, the non-invasive nature of most proposed procedures, the widespread prevalence of dance and exercise programs in the community, the general acceptance by practicing physicians of the procedures to be used, and the close supervision and monitoring of the subjects all minimizes the potential risks. Both dancing and walking may improve physical fitness, and involve minimal risks to the participant. Early diagnosis and treatment of disorders discovered as a result of screening done in these studies may impact beneficially on their health. In addition, understanding of the role of physical, mental, and social activities in ameliorating age-related cognitive decline could provide important insights into the aging process and age-related diseases that could ultimately have a positive impact on the length and quality of life for study subjects.

